DNA	Deoxyribonucleic acid
GCP	Good clinical practice
ECM	Embryo culture medium
ICH	International Council for Harmonization of Technical Requirements for Pharmaceuticals for Human Use
ICSI	Intracytoplasmic sperm injection
IEC	Independent ethics committee
IRB	Institutional review board
IVF	In vitro fertilization
IVI RMA	Instituto Valenciano de Infertilidade / Reproductive Medicine Associates
NMR	Nuclear magnetic resonance
PGT-A	Preimplantation genetic test for aneuploidy
SIVIS	Software for medical record management

AIM: main objective/research question

Main objective:

To evaluate whether nuclear magnetic resonance (NMR) spectroscopy can assist in the prediction of ploidy of pre-implantation embryos (euploidy vs aneuploidy).

Research question:

Is NMR able to identify a differential metabolic pattern between aneuploid and euploid embryos in order to improve embryo selection?

Is there a metabolic profile difference between an embryo with 3 days of culture and the same embryo after 5 or 6 days of culture?

Introduction

A. Background

Worldwide, infertility affects around 15% of the couples in reproductive age. The ability to procreate is largely a female-age limited process, with one in eight women experiencing infertility, a proportion that is even higher among women aged 35 or older. Assisted reproductive technologies (ART) are of paramount importance for these couples, and in many they are the only solution to constitute a family (1).

The optimal scenario in ART is a single-embryo transfer (SET) followed by the delivery of a healthy baby. For this reason, multiple laboratory technical approaches have been developed to improve the selection of the best embryo available. Currently, this selection process is largely based on morphologic assessment. This type of evaluation, however, appears to be insufficient since many apparently top quality embryos ultimately do not implant or eventually result in a miscarriage. One of the main reasons for this is the fact that up to 70% of the embryos considered viable from a morphological perspective present an abnormal number of chromosomes and are, therefore, generally not compatible with life (2).

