One means to overcome this issue is to perform preimplantation genetic testing of embryos to detect aneuploidy (PGT-A), which entails the removal of a small number of cells for analysis by either next-generation screening or comparative genomic hybridization (3). However, this analysis has the disadvantage of being invasive, time-consuming and expensive. Thus, the search for an efficient alternative selection method during the preimplantation stage which could improve the success rate of ART while decreasing the cost and time required to select chromosomally normal embryos as best as possible continues.

A suitable alternative to PGT-A could rely on the characterization of the metabolic profile of the embryo culture medium (ECM) by NMR, a non-invasive, rapid, economic and sensitive technique which is already currently clinically applicable. The conceptual basis of this approach has been described in a previous publication performed after a day 3 embryo biopsy, which demonstrated that embryos with chromosomal abnormalities presented a different metabolic pattern and, consequently, a different ECM composition (4). However, this study is of limited value, since it has been demonstrated that embryos are able to self-correct chromosomal errors found by day 3, whereby the current recommendation is for PGT-A to be performed on day 5 (or day 6). Further studies are needed to assess the usefulness of NMR for prediction of the ploidy of pre-implantation embryos.

B. Justification and translational potential to the clinic and impact on patient's care improvement:

This research study aims to validate the ECM analysis by NMR spectroscopy, as a faster and less-costly alternative to PGT-A which could significantly enhance embryo selection and the success rate of ART.

Methodology

A. Study Design

We propose a single-center prospective sibling case-control pilot study. In summary, all consenting patients will undergo in vitro fertilization (IVF) followed by PGT-A according to normal clinical practice. While the overall procedures towards PGT-A will not change, we will request that they consent additionally to donate the embryo culture medium, which otherwise would be discarded, for investigational purposes. The study will be conducted in conformance with Good Clinical Practices (GCP).

B. Study period and context

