Women who will undergo IVF followed by PGT-A at the Reproductive Medicine Clinic of IVI RMA Lisboa will be screened each day by a study collaborator and treating physician. Eligible women will be invited to participate in the study and provided written patient information on the trial (pre-screening visit). Those who accept to participate will be requested to sign written informed consent (screening/inclusion visit).

The on-study period is planned to have an overall duration of approximately 4 weeks with 2 visits for each subject, as detailed in Fig 1. The on-study period starts on the day that informed consent is signed, which can occur up to the day of patient oocyte retrieval, and ends when the results of the PGT-A procedure are known. More information regarding the overall recruitment plan, exposure, monitoring and data collection are described below.

[figure not shown]

Figure 1 – overall on-study period scheme

C. Reference Population

Our target population are healthy women who will undergo a IVF followed by PGT-A. This study will evaluate embryo culture medium compositions of 50 aneuploid embryos, 50 euploid embryos, and 30 controls (no-embryo culture medium).

D. Subject Inclusion/exclusion criteria and case-control matching

The subject inclusion and exclusion criteria are summarized in Table .

Inclusion criteria	Exclusion criteria

 Age: ≥ 18 and < 49 years old. Body Mass Index (BMI) ≥ 18.5 Kg/m² and < 30 Kg/m². Planned for IVF followed by PGT-A. Oocytes retrieval and fertilization by ICSI Six follicles over 14 mm on the day of the triggering. Signed and dated informed consent. 	
 Previous history of poor ovarian response (< 4 oocytes retrieved) with a maximal dose of ovarian stimulation (≥ 300 IU/day). Presence of a medical condition which is known to affect ART outcome (e.g. thyroid dysfunction). Current use of anti-depressants, anti-psychotics, steroids, antiepileptics or chemotherapy. Those unable to comprehend the investigational nature of the proposed study.

Table 1 – Study inclusion and exclusion criteria

E. Intervention and Follow-up

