Samples (ECM) will be collected and identified immediately using sticker labels. These labels contain a single anonymized identifying code with the following format: <STUDY CODE> <SUBJECT NUMBER> <TYPE OF SAMPLE> <SUBJECT YEAR OF BIRTH> <SAMPLE DATE>. For example, the identifying code 2004-LIS-037-SN-01-ECM_D3-1983-30042020 provides the following information:

- <STUDY CODE>: internal reference code of study (2004-LIS-037-SN)
- <SUBJECT NUMBER>: 0X
- <TYPE OF SAMPLE>: ECM_DX (X = day 3 or day 5/ day 6)
- <SUBJECT YEAR OF BIRTH>: coded as YYYY;
- <SAMPLE DATE>: date the sample was collected, coded as DDMMYYYY.

Statistical methodology

A. Data base

Data will be collected in a secure and encrypted case report form system created specifically for the study hosted on a dedicated server firewall-protected serve. The database will be rigorously defined with the variables destined to be analyzed according to the described study objectives and will have inbuilt validation procedures to ensure the correct introduction of data and avoid cases of missing information where such is not applicable. The study team collaborating in the study will be responsible for the data collection. These anonymized data will be stored for at least an additional 25 years.

In accordance with Portuguese law, all data exported for statistical analysis will be anonymized to protect the clinical and personal information of the subjects. Finally, and prior to the statistical study, an exploratory data analysis will be carried out to review the quality of the information extracted.

B. Study Variables

MAIN-OUTCOME MEASURES (DEPENDENT)

The primary outcome of this study is the assessment of different metabolic profiles between culture medium of euploid versus aneuploid embryos.

EXPOSURE VARIABLES (INDEPENDENT)

The metabolic profile of culture medium of euploid and aneuploid embryos will be compared to culture medium without embryo (control).

CONTROL VARIABLES

The following variables will be recorded during the analysis (as continuous variables, unless mentioned otherwise):

- Female subject age (in years).
- Male subject age (in years)
- Female body mass index.
- Menstrual cycle length.
- Number of preceding ART cycles.
- Duration of infertility (in years).
- Infertility diagnoses (tubal, ovulatory, endometriosis, male factor or otherwise unexplained).
- Baseline AMH.
- Baseline AFC.
- Number of follicles >11 mm on the day of ovulation triggering.

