- Total dose of exogenous gonadotropins.
- Total duration of OS.
- Number of oocytes retrieved.
- Number of fertilized oocytes.
- Number of embryos available for biopsy.
- Quality of each embryo available for biopsy.
- Number of euploid and aneuploid embryos.

C. Sample Size

Owing to the exploratory nature of the study, we are unable to determine an accurate sample size for this study hypothesis. Hence, we elected to recruit a pre specified number of a maximum of 50 subjects (donating a minimum of a pair of sibling culture media).

D. Statistical data analysis

EXPLORATORY DATA ANALYSIS

Basic demographic characteristics will be compared amongst the study who did and did not have a spontaneous miscarriage using the t-student/Mann-Whitney test (for continuous variables, according to the normality of the distribution) or Fisher's Exact test (for categorical variables).

HOMOGENEITY ANALYSIS

In order to minimize potential confounding, paired-sibling embryo culture media (two samples derived from the same patient and treatment cycle) will be allocated in pairs and in a 1:1 ratio to each study group. The pair-sibling allocation will be performing after the results of the PGT-A procedure are known.

OBJECTIVES ASSESSMENT

Considering that we will be able to identify around 20 to 30 metabolites, the minimum number of samples per group for a False Discovery Rate (FDR) of 5% is 40 samples, this value was calculated using the default parameters of MetSizeR (7), a software that allows sample size calculation for metabolomic studies. Assuming that a pre-specified proportion of at least 10% metabolites will be predictive of the outcome, the estimated power to detect a statistically significant difference among the groups is >90%.

Metabolite concentration will be used for univariate and multivariate analysis. In the univariate analysis, data normality will be checked by Shapiro test. Two-sample t-test, if the data has normal behavior, or Wilcoxon-rank test, if the data has not a normal behavior. Comparisons will be performed to confirm the metabolite differences significance. In multivariate analysis, sample classification will be performed by Principal Component Analysis (PCA), Partial Least Squares Discriminant Analysis (PLS-DA), and Orthogonal Projections to Latent Structures (OPLS-DA) using R and Simca.

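### The main objective is prediction of ploidy, but the plan sets no out-of-sample assessment of its classifiers and no accuracy measure, and the sibling-pair design requires that whole women be held out

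*Combined protocol and SAP*

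**What the plan says.** The AIM section gives the main objective: "To evaluate whether nuclear magnetic resonance (NMR) spectroscopy can assist in the prediction of ploidy of pre-implantation embryos (euploidy vs aneuploidy"). Introduction B goes further: "This research study aims to validate the ECM analysis by NMR spectroscopy" as an alternative to PGT-A. The primary outcome, in Study Variables, is narrower: "The primary outcome of this study is the assessment of different metabolic profiles between culture medium of euploid versus aneuploid embryos".

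The multivariate analysis is one sentence under Statistical data analysis, Objectives assessment: "sample classification will be performed by Principal Component Analysis (PCA), Partial Least Squares Discriminant Analysis (PLS-DA"). The same sentence names OPLS-DA as the third method, and R and Simca as the software. Nothing in the document adds cross-validation, a hold-out set, a permutation test, a rule for the number of components, or a measure such as AUC, sensitivity or specificity. The only validation procedures described are data-entry checks.

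Reference Population sets the samples at "50 aneuploid embryos, 50 euploid embryos, and 30 controls" without an embryo. Sample Size sets "a pre specified number of a maximum of 50 subjects". Methodology I pairs one euploid with one aneuploid sibling from the same woman and cycle, and allows up to three pairs per woman.

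**The concern.** A prediction objective is met by showing how well a rule classifies embryos it was not fitted to. PLS-DA and OPLS-DA choose their components to separate the known classes, so their fit to the same data is optimistic. With about 100 samples and 20 to 30 metabolites the optimism is not small. PCA does not use the class labels and is not a classifier.

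The design adds a second difficulty. Siblings share a woman and a cycle, and within each pair the labels are opposite. If cross-validation is added later in its ordinary form, with single samples held out, the held-out sample's sibling is usually still in the training set under the other label. The model then learns the woman's own profile with the wrong label attached.

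The first route can make NMR look useful when it is not; the second can make it look useless when it is not. Analysed and unused media are both destroyed (Methodology I), so the same media cannot be re-assayed later to settle the question.

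**Working it through.** **The plan's own figure.** Objectives assessment gives 40 samples per group at FDR 5%, with at least 10% of metabolites predictive and power above 90%. It cannot be rebuilt, because no effect size, SD or software settings are given. It can be bracketed:

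- Per-metabolite level: α* = FDR·π₁·power / [π₀·(1 − FDR)] = 0.05 × 0.10 × 0.90 / (0.90 × 0.95) = 0.00526.
- Detectable difference, two-sided and unpaired: d = (z for 1 − α*/2 + z for 0.90) × √(2/40) = (2.79 + 1.28) × 0.224 = 0.91 SD.
- Power at n = 40 is 29%, 78% and 95% for differences of 0.5, 0.8 and 1.0 SD.

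This figure concerns differences in single metabolites. It says nothing about classifier accuracy.

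**Inputs for the classifier check**

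- From the documents: 50 euploid and 50 aneuploid samples in opposite-label sibling pairs; 20 to 30 metabolites; one to three pairs per woman (50/3 = 16.7, so 17 women could supply all the pairs).
- Assumed: one to three components, sibling correlation r of 0 to 0.7, and correlation between metabolites of 0 to 0.6.

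**Method.** Each metabolite is √r × (woman effect) + √(1 − r) × (sample effect), with no ploidy effect. PLS-DA is fitted to autoscaled data. For one two-class response, OPLS-DA with the same total number of components gives the same predictions. AUC = [R₁ − n₁(n₁ + 1)/2] / (n₁n₀) = (R₁ − 1275)/2500, where R₁ is the rank sum of one class. AUC was computed on the fitted data, by 7-fold cross-validation of samples, and by 7-fold cross-validation of women, with 400 to 1,000 runs per setting.

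**Null results.** Mean AUC, with a true value of 0.50. Same-data figures are for 20–30 uncorrelated metabolites and 1–2 components; independent runs differed by about 0.01–0.02.

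| Sibling correlation | Same data | CV by sample | CV by woman |
|---|---|---|---|
| 0 | 0.74–0.80 | about 0.48 | about 0.50 |
| 0.5 | 0.67–0.74 | 0.31–0.35 | about 0.50 |
| 0.7 | 0.64–0.70 | 0.20–0.27 | about 0.50 |

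- *Smaller optimism.* One component with correlated metabolites, at sibling correlation 0.5, gives a same-data AUC of about 0.60–0.65.
- *Larger optimism.* If both sampling days entered one model (60 variables; sibling correlation 0.5, metabolite correlation 0.3), it is 0.67, 0.79 and 0.85 for one, two and three components.
- *One setting in detail* (25 metabolites, two components, sibling correlation 0.5, metabolite correlation 0.3). Same-data AUC averages 0.70 (5th–95th percentile 0.65–0.75), and half of the null studies reach 0.70 or more. By woman it averages 0.50 (0.40–0.59), and none of 1,000 reaches 0.70.
- *Fewer women.* With 17 women giving up to three pairs, the same setting gives 0.71 on the fitted data and 0.50 by woman.

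**Why cross-validation by sample falls below 0.50.** With seven folds of about 14 samples, the sibling of a held-out sample is in training with probability of about (100 − 14.3)/99 = 0.87, and its label is always the opposite one.

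**With a real signal** (assumed: 3 of 25 metabolites differ by 0.5 SD). At sibling correlation 0.5, cross-validation by sample gives an AUC of about 0.55 and by woman 0.66. At correlation 0 the gap nearly vanishes (0.63 and 0.64).

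**The case against.** The study calls itself a pilot and exploratory. Its declared primary outcome is a difference in profiles, which the univariate tests address. The word *validate* stands in the justification, not in the objective. These points lower the stakes, but prediction remains the main objective and nothing in the analysis plan measures it. Naming R and Simca fixes no validation scheme.

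A reader might infer that the plan guarantees a falsely useful classifier. The documents do not support that. They are silent on how performance will be judged; they do not say that same-data accuracy will be the result. The optimism also depends on unstated settings and is modest with one component, correlated metabolites or strongly similar siblings. Nor does the plan propose cross-validation by sample; that is a risk in filling the gap, and it matters only if siblings are correlated.

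Two further inferences go too far. One is that blank media will inflate accuracy: Study Variables compares embryo media with blanks, but nowhere are blanks said to enter the classifier as a class. The other is that 1:1 sampling will yield misleading predictive values: the plan promises none, and equal sampling does not by itself distort AUC, sensitivity or specificity.

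**Conclusion.** The gap is real. The prediction objective has no out-of-sample assessment and no named accuracy measure, and the paired design makes the choice of what to hold out decisive. If accuracy is read from the fitted data, noise can look predictive: mean AUC exceeded 0.50 in every setting tried, mostly lying between 0.60 and 0.80. If single samples are held out, the estimate falls below chance once siblings are correlated, and a real signal can be lost. Holding out whole women gave about 0.50 under the null throughout.

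The direction of each bias follows from the method and the design. The sizes rest on the assumed component counts, correlations and, for the signal case, effect size.

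**What to change.** In Statistical data analysis, Objectives assessment, state that:

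- classifier performance for euploid versus aneuploid embryo media is estimated by cross-validation with all samples of a woman in the same fold; blank media are not a class in this estimate;
- scaling and the choice of components are done inside the training folds;
- cross-validated AUC, sensitivity and specificity are reported, with confidence intervals resampled by woman;
- a permutation test swaps labels within pairs and repeats the whole procedure each time;
- PCA is used for description only.

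In Introduction B, replace *validate* with *explore*, since there is no independent test set. The choice between PLS-DA and OPLS-DA, and the number of permutations, can be left to the sponsor, provided both are fixed before the NMR data are analysed against ploidy.

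The change needs plan wording and a script, and no further patients, samples or procedures. The drawback is a little more analysis work and a lower reported accuracy than the fitted data would show.

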In order to minimize potential confounding, paired-sibling embryo culture media (two samples derived from the same patient and treatment cycle) will be allocated in pairs and in a 1:1 ratio to each study group. The pair-sibling allocation will be performing after the results of the PGT-A procedure are known. Pairing will be performed preferably using embryos with similar developmental staging and morphological grading.

Finally, each patient can include up to 3 pairs of sibling culture media in the analysis. The remaining samples will be immediately destroyed.

NMR procedure

ECM samples will be thawed at room temperature before analysis, will be transferred to a 1.7-mm NMR capillary shigemi tube for analysis. The NMR spectra will be acquired in a BrukerAvance II 500 spectrometer (BrukerBiospin) equipped with a prodigy TCI cryoprobe. All experiments will be acquired at 298 K. For each sample, two ¹H-NMR spectra will be obtained: a Carr-Purcell-Meiboom-Gill (CPMG) spin echo pulse sequence, which generates spectra edited by T2 relaxation times to reduce signals from high molecular weight species and to facilitate the detection of low molecular weight species, and a 1D NOESY pulse sequence, which generates an unedited spectrum with improved solvent peak suppression (extremely useful for the observation of signals near the water resonance). The spectra will be processed by a Fourier Transform and multiplied by an exponential function using Topspin 4.0. Phase correction, baseline correction and spectra calibration (methyl group signal of the lactate at a chemical shift 1.32 ppm) will be performed before further analysis. Metabolites will be quantified with ChenomxNmrSuite 8.0.2 using the Human Metabolites Database as reference. This software allows the deconvolution of the NMR spectra and the determination of the

metabolite concentrations. From the previous studies it is expectable that we will be able of determine around 20 to 30 metabolites including aminoacids, fatty acids and carbohydrates like sucrose, glucose and pyruvate.

The samples analysed in this study will be destroyed immediately upon analysis.

SAMPLE IDENTIFICATION PROTOCOL

All consenting subjects will be given a unique screening number (eg. 037-SN-0X). Each participant will be assigned only one screening number. Screening numbers will not be re-used for different participants.

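### The multivariate analysis pools samples across women and does not use the sibling pairing, so it does not directly address choosing between one woman's embryos; held-out within-pair ranking should be reported alongside per-embryo performance

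*Combined protocol and SAP*

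**What the plan says.** - **Purpose.** The first research question (AIM section) asks "Is NMR able to identify a differential metabolic pattern between aneuploid and euploid embryos in order to improve embryo selection". The main objective in the same section is to help predict ploidy, and the justification section presents NMR as a possible alternative to PGT-A.
- **Design.** Study Design calls this a "single-center prospective sibling case-control pilot study". The section on selecting sibling culture media says that "paired-sibling embryo culture media (two samples derived from the same patient and treatment cycle) will be allocated in pairs and in a 1:1 ratio" to the study groups. It adds that "Pairing will be performed preferably using embryos with similar developmental staging and morphological grading" and that "each patient can include up to 3 pairs of sibling culture media in the analysis". Samples left over after pairing are destroyed.
- **Size.** Reference Population gives 50 aneuploid and 50 euploid embryos. Sample Size gives at most 50 women with at least one pair each.
- **Analysis.** Objectives assessment says that "sample classification will be performed by Principal Component Analysis (PCA), Partial Least Squares Discriminant Analysis (PLS-DA"), with OPLS-DA as a third method. Neither the pair nor the woman enters this step. No AUC, sensitivity, specificity, within-pair measure, cross-validation or permutation test is named.

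**The concern.** The pairing is built in at sampling and then not used in the predictive analysis. Anything the two siblings share (the woman, the cycle and, where common to both, the medium lot or storage) moves both scores together. Across all women it blurs the separation of euploid from aneuploid, but it cancels when one sibling is compared with the other. Picking an embryo for transfer is a comparison of that second kind. A pooled summary alone could therefore make a score look weaker for selection than it is. And because no held-out scoring is named, a pooled summary computed on the training data could make a worthless score look good. In either case the embryo-selection question would be left without a direct answer, although the data can supply one.

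**Working it through.** **1. The plan's own figure.** The only quantitative claim is 40 samples per group at a 5% FDR with power above 90%, from MetSizeR defaults. No effect size or SD is given, so it cannot be reproduced forward. Working backward, the per-test alpha implied by the FDR is FDR·m1·power / ((1−FDR)(m−m1)):
- m = 20, m1 = 2: 0.05·2·0.9 / (0.95·18) = 0.0053
- m = 25, m1 = 2: 0.05·2·0.9 / (0.95·23) = 0.0041

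A two-sample t-test with 40 per group then has 90% power at a standardised difference of about 0.93-0.95. This neither supports nor contradicts the present point.

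**2. One score, closed form.** Let d be the euploid-aneuploid difference in units of the total SD, and r the correlation between siblings.
- Pooled AUC = Φ(d/√2)
- Probability that the euploid sibling scores higher = Φ(d/√(2(1−r)))

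Neither d nor r is in the documents, so both are assumed.

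| d | Pooled AUC | Pair, r=0 | r=0.2 | r=0.4 | r=0.6 |
|---|---|---|---|---|---|
| 0.5 | 0.638 | 0.638 | 0.654 | 0.676 | 0.712 |
| 0.8 | 0.714 | 0.714 | 0.736 | 0.767 | 0.814 |

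The gap is zero at r = 0 and grows with r.

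**3. PLS-DA simulation.** From the documents: 50 pairs (taken as one per woman), 25 metabolites (the plan expects 20 to 30), 3 of them informative (12%; the plan assumes at least 10%). Assumed: independent metabolites, between-woman variance share r, and a within-pair difference of 0.5 SD of the pair difference. With total variance 1 that shift is 0.5·√(2(1−r)). The model has two components and 10-fold cross-validation with whole women held out.

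| r | Held-out accuracy | Held-out pooled AUC | Held-out pairs ranked correctly | Apparent AUC, no signal |
|---|---|---|---|---|
| 0 | 66% | 0.72 | 72% | 0.79 |
| 0.3 | 64% | 0.69 | 72% | 0.75 |
| 0.5 | 62% | 0.66 | 73% | 0.72 |
| 0.7 | 59% | 0.62 | 72% | 0.68 |

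The last column is training-data AUC when no metabolite differs. Held-out measures then average about 0.50.

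**4. The right comparator.** Accuracy at a cut-off and a two-way choice are on different scales. For a single normal score, 72% pair ranking with no clustering corresponds to Φ(Φ⁻¹(0.72)/√2) = Φ(0.583/1.414) = 66% accuracy. So about 6 points of any accuracy-versus-ranking gap come only from the change of metric. AUC is the like-for-like comparison: the gap is 0 at r = 0, then about 4, 6 and 10 points.

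**5. A second parameterisation.** Holding the difference at 0.5 of the total SD, with correlation 0.3 between metabolites, held-out AUC against pair ranking is 0.665 vs 0.669 (r = 0), 0.696 vs 0.750 (r = 0.4) and 0.704 vs 0.808 (r = 0.6). The direction is the same. At r = 0.4 the apparent AUC is 0.82, above the held-out pair figure of 0.75.

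**6. Precision.** 36/50 pairs gives an exact 95% interval of 57-84%, about ±13 points. Excluding 50% takes at least 33/50 (one-sided exact p = 0.016). That rule has power 51% at a true 65%, 78% at 70% and 94% at 75%. These figures assume one pair per woman. At up to three pairs each, 50 pairs could come from as few as 17 women (50/3 = 16.7).

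**The case against.** The main objective is to predict ploidy, and the intended use is an alternative to PGT-A. Both need a label for each embryo, and a woman may have no euploid embryo to choose. This stands: per-embryo classification belongs in the plan, and within-pair ranking should sit beside it, not replace it as the headline.

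A forced choice within a 1:1 pair, preferably matched on stage and grade, is also not a real cohort, and destroying unpaired samples rules out ranking whole cohorts. That stands as a limit on interpretation. The study is an exploratory pilot, and pair ranking could be computed later from the same scores. That lowers the urgency, but fixing the measure now avoids choosing among methods and metrics after seeing the data.

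Several stronger readings are tempting and are not supported:
- *Pooled analysis necessarily understates performance.* This needs positive sibling correlation and held-out scores. The documents quantify neither, and without validation the error runs the other way.
- *Within-pair ranking is the only accuracy measure the design allows, or the only one free of prevalence.* Sensitivity, specificity and AUC against PGT-A can all be estimated in the sampled embryos, and none depends mathematically on the 1:1 ratio. Predictive values do.
- *Pair ranking has more power.* In simulations of the step 3 kind, pooled AUC beat chance with 88-92% power against 83-84% for pair ranking.
- *The plan applies one cut-off to all women.* It names no cut-off.

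**Conclusion.** The concern holds in a limited form. The multivariate plan drops the pairing that the design creates and names no performance measure, so its output does not directly address choosing between siblings. Under the step 3 assumptions, held-out pooled AUC sits about 4 to 10 points below within-pair ranking when the between-woman share is 0.3 to 0.7, and the two agree when it is zero. The plan pairs siblings to limit confounding, which suggests shared variation is expected, but its size is unknown. The simulations show direction and order of size only. The lack of held-out scoring is at least as consequential: apparent AUC of 0.68-0.79 can arise from no signal. This is a cheap improvement to the reporting of a pilot, not a flaw that invalidates it.

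**What to change.** Add to Objectives assessment:

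> PLS-DA and OPLS-DA classify each embryo as euploid or aneuploid. Performance is estimated with all samples from a woman held out together and reported as AUC, sensitivity and specificity against PGT-A. Alongside these we report the proportion of held-out euploid-aneuploid sibling pairs in which the euploid embryo has the higher euploid score (chance 50%), with a 95% confidence interval clustered by woman. PCA is used only to inspect outliers and batch effects.

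PCA is unsupervised and does not itself classify, hence the last sentence. The pair link must also be recorded: the listed fields of the sample code (study, subject, sample type, birth year, date) include no embryo number, so siblings sampled on the same day would share a code.

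The cost is a short paragraph, an embryo identifier and some cross-validation code, with no new samples or assays. The downside is a wide interval, about ±13 points at 50 pairs, and a measure that is only a proxy for selection in a full cohort and says nothing about a lone embryo.
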